ORAL MILETOSINE plus INTRALESIONAL PENTAMIDINE FOR BOLIVIAN CUTANEOUS LEISHMANIASIS

1. Introduction

1.1 Background

Cutaneous leishmaniasis (CL) is endemic in the New World from approximately the US-Mexican border through Central America and the Northern part of South America down to the level of Rio de Janeiro.

The cure rate for New World CL is only approximately 70% for all recognized therapies. For systemic therapy with the classic agent pentavalent antimony, recent cure rates of New World CL are 50% to 75% [1-5]. For the new oral agent miltefosine in 3 of these studies, the cure rate was 57-75% [2-4]. CL can also be treated locally. For intralesional (IL) antimony, cure rates are reported as 56-75% for Iranian CL [6-7], 80-83% for *L braziliensis* in Brazil [8-9], and most recently 70% for *L braziliensis* in Bolivia when the concomitant placebo cure rate was 18% [10].

A novel approach was to evaluate intralesional pentamidine for Bolivian CL. The rationale for IL pentamidine is that little drug is administered via intralesional injection, thus the toxicity of systemic pentamidine would be unlikely to be seen. For Bolivian CL, 3-injections of IL Pentamidine over 5 days cured 72% of patients whereas 3-injections of IL antimony over 5 days cured 57% [manuscript submitted]. Adverse effects were local irritation and injection site pain: IL pentamidine (30 patients)—mild (4 patients), moderate (3); IL antimony (60 patients)—mild (25 patients), moderate (4). No pentamidine patient experienced the side effects of systemic pentamidine administration: sterile abscess, hypotension, or hypoglycemia. We concluded that IL pentamidine is an attractive alternative to standard intralesional antimony for Bolivian *Leishmania braziliensis* on the basis of efficacy, the threat of antimony-resistant parasites, tolerance, and patient convenience of 3 visits over 5 days.

1.2 Rationale

Although patients can be treated with one of these agent with the anticipation of an approximately 70% cure rate, and failures of the first treatment could then be treated with another agent, an initial cure rate > 70% would be desirable.

We propose to evaluate oral miltefosine plus intralesional pentamidine for Bolivian CL. Efficacy should be additive, since the postulated mechanisms of the drugs is different. The structure of miltefosine is similar to that of phosphatidylcholine, and may interfere with phosphatidylcholine biosynthesis or function[11]. In contrast, it is thought that pentamidine interferes with polyamine biosynthesis [12]. The advantage of the combination of oral miltefosine and IL pentamidine vs other possible drug combinations is that the systemic partner is oral rather than parenteral, and that the intralesional partner is the most active of the IL agents that we have found in Bolivia. The combination should be well tolerated, since the local side effects of pentamidine would not interact with the systemic gastrointestinal side effects of miltefosine. Finally, this combination would be

convenient, since intralesional injections of pentamidine would occur on days 1, 3, and 5 of the standard 28-day miltefosine treatment course when patients are already under medical care.

2.0 Study Aims and design

2.1 Aim:

The primary purpose of this study is to evaluate the cure rate of a standard course of oral miltefosine in combination with intralesional pentamidine for single lesions predominately due to *L braziliensis* in Bolivia.

A secondary purpose is to determine the tolerance of this regimen.

2.2 Design:

Open label evaluation of miltefosine (28 days) plus intralesional pentamidine (days 1, 3, 5).

After treatment, all patients will be followed for 1, 3, and 6 months.

The initial number of patients will be 30.

3.0 Experimental Plan

3.1 Site

Catchment area: **Nor Yungas, Departamento de La Paz** Bolivia

Treatment site: **Hospital Local Palos Blancos** Bolivia. The patients will be in residence at the treatment site during treatment.

3.2 Study Population (inclusion and exclusion criteria)

Gender: Male or female

Age: ≥ 12 yrs of age

Presentation: 1 ulcerative lesion, ≤ 30 mm in largest diameter, and with a total lesion area ≤ 900 mm².

Parasitology: Parasitological confirmation of the lesion will be made by visualization or culture of leishmania from the biopsy or aspirate of the lesion.

Previous treatment for leishmaniasis:

No specific or putatively specific therapy (Sb, pentamidine, amphotericin B, miltefosine, imidazoles, allopurinol) in the last 3 months

Other diseases: No concomitant diseases by history that would be likely in the PI's opinion to interact, either positively or negatively, with treatment.

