3.3 Study treatments

3.3.1 Miltefosine

Miltefosine will be administered daily for 28 days as per the US Product Label:

“Administer with food to ameliorate gastrointestinal adverse reactions.

- 30 to 44 kg: one 50 mg capsule twice daily for 28 consecutive days.
- 45 kg or greater: one 50 mg capsule three times daily for 28 consecutive days.”

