3.6 Procedural Timetable

Action	Day 0	Day 1	Day28	1 M	3 M	6M
Consent	X					
Hx /PE	X		X	X	X	X
Parasitology (aspirate:smear/cult)	X					
Evaluate lesion	X	X	X	X	X	X
Treatment						
Oral Miltefosine			day 1 to day 28			
IL pentamidine			days 1, 3, 5			
Adverse events (esp. GI)	X	day 1	to day 28			
Blood Glucose	X	weeks 2	and 4			
AST	X	weeks 2	and 4			
Creatinine	X	weeks 2	and 4			

“Day 0” includes the screening period.

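### Section 3.2 admits females from age 12 with no pregnancy or breastfeeding criterion, and 3.6 schedules no specific check before a 28-day oral course

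*Protocol*

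**What the plan says.** Section 3.2, headed as the inclusion and exclusion criteria, lists six items. Two define the demographic range: "Gender: Male or female" and "Age: ≥ 12 yrs of age". Three concern the lesion, its parasitological confirmation and recent antileishmanial therapy. The sixth is the only general health exclusion: "No concomitant diseases by history that would be likely in the PI's opinion to interact" with treatment.

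The section 3.6 timetable marks the screening work under Day 0, which by its footnote "includes the screening period". No separate screening visit is scheduled.

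On treatment, section 3.3.1 states: "Miltefosine will be administered daily for 28 days as per the US Product Label". The label text it then reproduces covers taking the drug with food and the dose by weight band.

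Two passages give the reasons for expecting the combination to be safe. Section 1.1 argues that "little drug is administered via intralesional injection, thus the toxicity of systemic pentamidine would be unlikely to be seen". Section 1.2 says: "The combination should be well tolerated, since the local side effects of pentamidine would not interact" with the gastrointestinal effects of miltefosine.

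**The concern.** Section 3.2 expressly includes women and girls of childbearing age, and the trial gives them a systemic drug for four weeks. In that setting the entry rules would be expected to say whether pregnant or breastfeeding patients may enter, and the screening schedule to say how their status is established. Neither section does. If the omission is real, a pregnant or breastfeeding patient satisfies every written criterion, and an investigator who follows the protocol has no stated ground for keeping her out. What is at stake is exposure of a fetus or infant for which the protocol offers no supporting safety information. The estimate of the cure rate is not at stake.

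**Working it through.** The plan states no figure on this point to reproduce. The check is a reading of the eligibility, treatment and screening text, plus one dose calculation.

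**1. Eligibility (section 3.2).** The headings are gender, age, presentation, parasitology, previous treatment and other diseases. Headings that name pregnancy or breastfeeding: 0 of 6. The nearest candidate is the last, but it fails on two counts. It covers diseases, and pregnancy and lactation are not diseases. Its test is also interaction with treatment, not harm to a fetus or infant.

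**2. Screening (section 3.6).** The items marked at Day 0 are consent, history and physical examination, parasitology, lesion evaluation, adverse events, blood glucose, AST and creatinine. Items that name pregnancy or breastfeeding: 0 of 8. The history and examination might bring a pregnancy to light, but no item asks for it, and 3.2 contains no rule that would then exclude the patient.

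**3. Exposure (section 3.3.1).** Total oral miltefosine = capsule strength × capsules per day × days.

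| Weight band | Calculation | Total |
|---|---|---|
| 30 to 44 kg | 50 mg × 2 × 28 | 2800 mg |
| 45 kg or more | 50 mg × 3 × 28 | 4200 mg |

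These totals describe the course such a patient would receive. They do not measure risk, because the protocol gives no threshold to compare them with.

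**4. Does the safety reasoning reach this case?** The argument in section 1.1 rests on the small amount of drug given by local injection. It applies to pentamidine and cannot be carried over to the oral drug. The argument in section 1.2 is that two kinds of side effect in the treated patient, local and gastrointestinal, should not compound each other. Neither addresses exposure in pregnancy or lactation.

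**5. Does another provision act as an entry rule?** Section 3.8 lets the physician or patient end participation when they think it advisable. That is discretion after entry. The label reference in 3.3.1 stands under treatment and introduces food and dosing instructions; it adds no criterion to 3.2.

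**The case against.** The textual omission is hard to dispute. The strongest reply concerns how much it matters.

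- **No hazard is documented.** The protocol nowhere says that either drug is harmful in pregnancy or lactation; the only miltefosine toxicity it names is gastrointestinal. This stands. The point rests on the absence of any safety information for these patients, not on a known toxicity, and it assumes nothing about what the label says.
- **The label may cover it.** A clinician could read the label reference in 3.3.1 as importing all conditions of use. The label is not in the document, so its content cannot be settled here. Even on that reading, the entry criteria and the screening schedule stay silent.
- **Safeguards may exist elsewhere.** Some text between sections 4.2 and 5.4 was not available for this review. Section 5.5 describes ethical approval as an extension of an earlier protocol of intralesional treatments, which was also not available. Either might contain relevant wording, so whether such a patient would in practice be treated is unverified. Neither changes 3.2 or 3.6 as they read, and the earlier protocol, as named, concerns intralesional drugs and not oral miltefosine.
- **Patients are supervised.** They live at the hospital during treatment, are examined at Day 0 and can be withdrawn. This lowers the practical risk but does not replace an entry criterion.
- **A history question is a weak screen.** It can miss an early, unrecognised pregnancy, and it does nothing about conception during or after treatment. This also stands, as a limit of the minimal fix.

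Deferral to a statistical analysis plan is no answer, because eligibility and screening belong in the protocol.

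**Conclusion.** The concern holds. As written, section 3.2 admits a pregnant or breastfeeding patient to a 28-day systemic course of 2800 or 4200 mg, and section 3.6 schedules nothing specific that would identify her. This is an entry rule drawn too broadly, not a detail left for later.

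The conclusion is limited to 3.2 and 3.6. It does not claim that the trial has no safeguard elsewhere. The document gives no sex ratio or pregnancy rate, so no number of affected patients among the initial 30 can be stated, and it could be none. The severity of harm cannot be established from the document either. The change is worth making on safety grounds because it closes the gap in the written entry rule at very little cost; confidence in the importance of the point is moderate.

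**What to change.** Add one line to section 3.2: *Not pregnant and not breastfeeding.* In section 3.6, have that status asked and recorded as part of the history already taken at Day 0. The sponsor should check the wording against the US Product Label cited in 3.3.1, and should decide at the same time whether a history question is enough or whether a pregnancy test and a rule on contraception are also needed.

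The minimal change costs one eligibility line and one question at an existing visit. Its downside is that a few otherwise eligible patients may be excluded. A test or a contraception rule would cost more than this.

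### Section 3.2 admits patients from age 12 with no weight criterion, but section 3.3.1 states a miltefosine dose only from 30 kg, so an eligible patient under 30 kg has no protocol dose

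*Protocol*

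**What the plan says.** Section 3.2 is the protocol's list of inclusion and exclusion criteria. Two of its lines describe the person rather than the disease: "Gender: Male or female" and "Age: ≥ 12 yrs of age". The others cover the lesion (a single ulcer within stated limits of diameter and area), parasitological confirmation, recent antileishmanial treatment, and other illness. The only line that leaves room for judgement is the last: "No concomitant diseases by history that would be likely in the PI's opinion to interact", in either direction, with treatment. Body weight does not appear.

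Section 3.3.1 takes its dose from an outside source, "Miltefosine will be administered daily for 28 days as per the US Product Label", and then reproduces two weight bands: "30 to 44 kg: one 50 mg capsule twice daily for 28 consecutive days" and "45 kg or greater: one 50 mg capsule three times daily for 28 consecutive days". It gives no regimen below the first band and no rule for rounding weight.

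Section 2.2 sets the size of the study: "The initial number of patients will be 30".

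**The concern.** Entry depends on age and the miltefosine dose depends on weight, and no line connects the two. Followed literally, the entry rule can admit someone for whom the treatment rule has no answer. The lower age limit is 12, and it is among the youngest patients that a weight under 30 kg is most plausible.

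Two things are at stake. The first is safety: the undefined element is a 28-day systemic course, and the person concerned would most likely be an adolescent. The second is the clarity of the population. Section 2.1 aims to estimate the cure rate of a standard miltefosine course combined with intralesional pentamidine, with tolerance as the secondary purpose. That requires the patients who may enter and the patients for whom the course is defined to be the same group. As written, the first group is wider than the second.

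This is not a matter that could be left to a statistical analysis plan. Eligibility and dosing belong in the protocol, and this protocol fixes both, in ways that do not fit together.

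**Working it through.** The protocol states no figure to reproduce. The check compares the weights that 3.2 admits with the weights that 3.3.1 covers.

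**Inputs**
- Entry criteria (3.2): sex, age, lesion, parasitology, previous treatment, concomitant disease. None refers to weight.
- Lower dose band (3.3.1): 30 to 44 kg.
- Upper dose band (3.3.1): 45 kg and above.

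**Comparison**

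| Weight of a patient aged 12 or over | Admitted by 3.2? | Miltefosine dose in 3.3.1? |
|---|---|---|
| under 30 kg | yes | none stated |
| 30 to 44 kg | yes | lower band |
| above 44 and below 45 kg | yes | none stated, unless weight is in whole kilograms |
| 45 kg and above | yes | upper band |

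The first row is uncovered however weight is recorded. The third row is empty if weight is recorded in whole kilograms.

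**Could another section close the first row?**
- *Concomitant-disease line (3.2).* It concerns illness by history that might interact with treatment. Low body weight in an otherwise healthy adolescent is not such an illness.
- *Reference to the product label (3.3.1).* The protocol reproduces only these two bands and carries no weight limit from the label into 3.2. Whatever else the label says is outside the document.
- *Intralesional pentamidine (3.3.2).* This dose is set by lesion area, so it is defined for every eligible patient. The gap concerns miltefosine only.
- *Timetable (3.6).* It places history and physical examination at Day 0, which includes screening, but names no weight check for eligibility.
- *Early withdrawal (3.8).* It allows a patient to leave if the physician or patient thinks it advisable. That is a rule for leaving the study; it supplies neither an entry limit nor a dose.

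None of these sections resolves the mismatch.

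**The case against.** The strongest reply is that the mismatch may never matter in practice. Dosing is tied to the label, and nothing authorises a dose outside the bands shown. Day 0 comes before the first treatment day, and weight must be known to choose a band. A patient for whom no dose exists could therefore be recognised at screening and simply not started. The number affected may also be zero.

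Much of this stands, and it rules out several stronger readings that a reader might infer.

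- *That the site is forced either to improvise a dose or to lose a treated patient.* The protocol directs neither, and not starting the patient is open to it.
- *That patients under 30 kg would be over-exposed.* Each band peaks at 3.33 mg/kg/day by its own figures (2 × 50 mg / 30 kg; 3 × 50 mg / 45 kg). The lower-band regimen at 25 kg would give 100/25 = 4.0 mg/kg/day. But no passage says to give that regimen below 30 kg, and 25 kg is an arbitrary choice. The figure measures a hypothetical deviation, not something the plan prescribes.
- *That each such patient moves the cure rate by 1/30 = 3.3 percentage points.* Section 3.9 analyses the results once 30 patients have been evaluated. A patient who is never treated need not be among those 30, and the text does not rule out replacement.
- *That the step from 44 to 45 kg is a second dosing gap of equal weight.* The bands are quoted label text and most naturally read as whole kilograms. Only the absence of a rounding rule makes the point worth a word.

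What the reply does not do is make 3.2 and 3.3.1 agree. Turning away a patient who satisfies every written criterion means applying an entry rule that the protocol does not contain.

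**Conclusion.** The point holds in a limited form. Sections 3.2 and 3.3.1 are inconsistent for patients aged 12 or over who weigh less than 30 kg: they are eligible and have no stated miltefosine dose. That follows directly from reading the two sections together and needs no outside information.

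The practical size cannot be given. The protocol contains no weight data, so the expected number among the 30 patients first planned is unknown and may be zero. No effect on exposure or on the cure rate is established. The point merits correction because it concerns systemic dosing, probably in adolescents, and is cheap to settle before anyone is enrolled.

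The conclusion assumes that no weight criterion stands in the text between sections 4.2 and 5.4, which was not available for review. That would be an unlikely place for one. The 44 to 45 kg wording is secondary and disappears if weight is recorded in whole kilograms.

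**What to change.** Before enrolment, the sponsor should reconcile section 3.2 with section 3.3.1 so that every patient who meets the entry criteria has a stated miltefosine dose. Which section governs is a clinical decision for the sponsor; no dose and no weight limit is proposed here.

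In the same edit, state whether body weight is recorded in whole kilograms, so that the two bands leave no space between them. This can be done without altering the quoted label wording.

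The cost is about one line of text, and no additional measurement is needed, since weight must already be known to choose a band. Depending on the sponsor's choice, a few very light adolescents might become ineligible.

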3.3 Study treatments

3.3.1 Miltefosine

Miltefosine will be administered daily for 28 days as per the US Product Label:

“Administer with food to ameliorate gastrointestinal adverse reactions.

- 30 to 44 kg: one 50 mg capsule twice daily for 28 consecutive days.
- 45 kg or greater: one 50 mg capsule three times daily for 28 consecutive days.”

3.3.2 IL pentamidine

IL pentamidine [Pentacarinat® Sanofi-Aventis: 30 mg/ml] will administered at a dose of 120 ug (4 ul) per mm² of lesion area 3 times (on days 1, 3, and 5) as per our previous experience.

A small button of Xylocaine® will be applied by means of a thin needle at the four cardinal points of the lesion and then a small gauge (23g) needle will introduce the drug in each cardinal point. The needle will be moved in all directions to infiltrate of whole lesion and surrounding infiltrated area.

3.3.3 Pretreatment

If bacterial superinfection appears to be present, the lesions will receive topical fusidic acid and/or oral dicloxacillin during 7 days previous to the first day of leishmania treatment. Initial size will be measured after the antibacterial treatment.

3.4 Efficacy evaluation

For each lesion, the size of its ulcer will be measured at 1 month, 3 months, and 6 months after the end of therapy.

3.5 Adverse events recording

Re Miltefosine: Adverse events especially gastrointestinal will be recorded.

Re IL pentamidine: Patients will be evaluated for local side effects (pain, itching, irritation (erythema/edema), vesicles/bullae, sterile abscesses) and the possibility of bacterial superinfection both local and disseminated to the draining lymph nodes on each day that therapy is applied. Any other subjective complaint spontaneously referred by the patient will be registered and evaluated.

In addition, pentamidine patients will be evaluated for hypoglycemia.

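### No blood glucose is scheduled on days 1 to 5, when pentamidine is injected, so the hypoglycemia evaluation has no measured value for that period

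*Protocol*

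**What the plan says.** Section 3.5 ends its account of adverse event recording with "In addition, pentamidine patients will be evaluated for hypoglycemia". The sentence stands by itself. The preceding requirement to examine patients on every treatment day concerns local reactions and bacterial superinfection.

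Section 3.3.2 gives the injections "3 times (on days 1, 3, and 5) as per our previous experience". The glucose row of the section 3.6 timetable reads "Blood Glucose X weeks 2 and 4", and the AST and creatinine rows carry the same entry. Day 0 is defined there as including screening, so it precedes the first injection.

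Three other statements bear on the point. Section 3.1 says "The patients will be in residence at the treatment site during treatment". The adverse event row in 3.6 reads "Adverse events (esp. GI) X day 1 to day 28". Section 1.1 says of the earlier intralesional study: "No pentamidine patient experienced the side effects of systemic pentamidine administration: sterile abscess, hypotension, or hypoglycemia". That study had 30 patients in its pentamidine group. Tolerance is a declared aim in section 2.1: "A secondary purpose is to determine the tolerance of this regimen".

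**The concern.** The protocol's only stated reason for looking for hypoglycemia is pentamidine, and pentamidine is given only in the first five days. Glucose instead follows the calendar of the other laboratory tests. A trial run exactly to the timetable would end with no glucose value from the injection period.

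What is at stake is what can be said about tolerance. If the report states that no hypoglycemia occurred, that statement would rest on symptoms alone for days 1 to 5, while the scheduled glucose results could give the impression that it had been measured. An analysis plan cannot repair this afterwards, because the samples would not exist. The cure endpoint is not touched.

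**Working it through.** The protocol gives no figure of its own to reproduce. The check compares two sets of days and then looks at dose and earlier experience.

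**Days.** Injections (3.3.2, 3.6): days 1, 3, 5. Glucose (3.6): Day 0, week 2, week 4. The protocol does not define its weeks. Counting day 1 as the start of week 1, week 2 is days 8 to 14 and week 4 is days 22 to 28.

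| Glucose test | Days | Days after last injection (day 5) |
|---|---|---|
| Day 0 | before day 1 | none given yet |
| Week 2 | 8 to 14 | 8 − 5 = 3 to 14 − 5 = 9 |
| Week 4 | 22 to 28 | 22 − 5 = 17 to 28 − 5 = 23 |

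Injection days with a scheduled glucose: 0 of 3. Scheduled tests after the start of treatment: 2 × 30 = 60, of which 0 fall on days 1 to 5.

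**Table layout.** In the extracted table, part of the glucose entry sits under the Day 1 heading. AST and creatinine show the same layout, so the entry reads as weeks 2 and 4 and not as a Day 1 test.

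**Dose.** Section 3.3.2 sets 120 µg per mm² and section 3.2 allows one lesion of at most 30 mm diameter and 900 mm².
- At the area limit: 900 × 120 µg = 108,000 µg = 108 mg per injection.
- For a circular lesion 30 mm across: π × 15² = 707 mm²; 707 × 120 µg ≈ 85 mg per injection.

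These are maxima for the largest eligible lesions. The documents do not say what such a dose does to glucose.

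**Earlier experience.** Section 1.1 reports no hypoglycemia in 30 patients. The exact upper 95% limit for 0 of n is 1 − α^(1/n), with α = 0.05 one-sided and 0.025 two-sided.
- One-sided: 1 − 0.05^(1/30) = 0.0950, or 9.5%.
- Two-sided: 1 − 0.025^(1/30) = 0.1157, or 11.6%.

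Section 1.1 does not say how or when glucose was checked, so these limits take its zero at face value.

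**The case against.** The strongest reply is that the documents give no time course for a fall in glucose, so nothing in them proves that days 1 to 5 are the right window. Patients are resident, adverse events are recorded from day 1 to day 28, and spontaneous complaints are registered and evaluated. Section 1.1 expects systemic toxicity to be unlikely by this route and reports none. No decision depends on glucose: section 3.9 ties further enrolment to the cure rate. The timetable is also not an exhaustive list, since the examinations for local effects on injection days have no row of their own.

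Much of this stands. The likelihood of a missed fall is unknown, and symptomatic episodes can be noticed. The time-course point, however, does not justify having no measurement at all near the exposure that prompts the evaluation. Nor does an incomplete timetable help: the examinations for local effects are assigned to injection days in the text of 3.5, whereas the hypoglycemia sentence is assigned to no day anywhere in the available text.

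Two stronger readings are tempting. A reader might infer that 3.5 and 3.6 contradict each other. They do not, because 3.5 promises an evaluation without promising a glucose test on any day. A reader might also infer that hypoglycemia on injection days would go undetected or that patients are left unsafe. The documents do not support that either, given residence and daily adverse event recording. Nor do they support the inference that the earlier 30 patients were judged by symptoms alone; section 1.1 is silent on the method.

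**Conclusion.** The concern holds in a limited form. The schedule is poorly matched to the exposure it is meant to monitor: 0 of 3 injection days have a glucose test, and the first later value comes 3 to 9 days after the last injection. That interval assumes the week numbering above. What is lost is measured evidence on asymptomatic or transient falls in days 1 to 5, for the secondary tolerance aim only. The gap in the schedule is clear from the text; its clinical importance cannot be judged from the documents. Earlier experience lowers the concern without settling it, since 0 of 30 is compatible with a true rate of about 10%. The point merits correction because the remedy costs very little.

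**What to change.** In section 3.6, replace the glucose entry with: Day 0; day 5, at a fixed time after the third injection; week 2. The sponsor should choose the time and write it in, because the documents give no basis for a particular hour and an unspecified time could miss a transient fall. The week 4 test is the one to move, since it is furthest from pentamidine exposure. Day 5 is proposed because all three doses have then been given.

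In section 3.5, add that patients will be asked about symptoms of hypoglycemia on days 1, 3 and 5, and that glucose will be measured on day 5 at the stated time and at week 2.

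The number of tests is unchanged: 3 per patient, 3 × 30 = 90 in all. Tests on days 1 to 5 rise from 0 to 30, one per patient. The costs are the loss of the week 4 glucose and one extra sampling occasion per patient, because AST and creatinine stay at week 4. Days 1 and 3 would still be covered by symptoms only. If the sponsor wishes to keep week 4 as well, a day 5 test can be added for 30 further tests.

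If no test is moved or added, state in 3.5 that hypoglycemia on days 1 to 5 is judged by symptoms only, and make no glucose-based claim for those days. That costs one sentence.
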